11.1.2 Methods and Timing for Capturing and Assessing Safety Parameters

The CC is responsible for ensuring that all SAEs related to pregnancy, pregnancy outcomes, and infants, as well as the following non-serious AEs during the neonate’s/infant’s first year of life: severe infections of NCI CTCAE severity Grade 3, neutropenia, lymphopenia, leukopenia, thrombocytopenia, decreased B-cell counts, hypogammaglobulinemia, and inadequate vaccine response, including low vaccine-induced response titers, are reported by HCPs as per protocol (see [Section 11.1.1.1](#) for definition) and are recorded in the eCRF.

Once the patient is enrolled in the study, SAEs related to pregnancy will be collected until the end of her observation period, i.e. until a pregnancy outcome is reported, unless the patient withdraws from the study prematurely. SAEs and the selected non-serious AEs described above experienced by the infant will be reported until the first year of life.

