 - Pregnancy outcome, if applicable (e.g., elective or therapeutic termination, spontaneous abortion, ectopic pregnancy, molar pregnancy) as per [Section 9.3.2](#)

- Reason for elective or therapeutic termination (e.g., prenatal testing finding, risk to mother's health, undesired pregnancy), if applicable
 - Autopsy results and pathology reports, if available
- Changes in MS disease status (including treatment changes and relapses, EDSS score)
- Ocrelizumab treatment (including start and stop dates, dose, dosing frequency, reason for discontinuation [if applicable])
- Changes in comorbid conditions
- Current lifestyle factors (e.g., smoking, caffeine consumption, alcohol use, illicit drug use)
- Current medications (including other MS treatments such as glatiramer acetate, teratogenic medications or medication with potential fetal health implications, corticosteroids, folic acid, other vitamins and supplements, vaccinations, medications to treat other chronic diseases)
- SAEs related to pregnancy (as per [Section 11](#))

Birth outcome follow-up (approximately 4 weeks after EDD):

- Date of contact and date of pregnancy outcome or gestational age (in weeks)
- Changes in contact information; contact information for infant's HCP
- Reporter of information (patient, obstetrician, infant HCP)
- Pregnancy outcome (as per [Section 9.3.2](#), e.g., live birth, stillbirth, spontaneous abortion, elective or therapeutic termination):
 - Reason for elective or therapeutic termination (e.g., prenatal testing finding, risk to mother's health, undesired pregnancy), if applicable
 - Autopsy results and pathology reports, if available
- Mode of birth (vaginal delivery, assisted delivery/cesarean section, type of anesthesia)
- MS disease and treatment status since last follow-up
- Ocrelizumab treatment (including start and stop dates, dose, dosing frequency, reason for discontinuation [if applicable])
- Changes in comorbid conditions
- Current lifestyle factors (e.g., smoking, caffeine consumption, alcohol use, illicit drug use)
- Current medications (including other MS treatments such as glatiramer acetate, teratogenic medications or medication with potential fetal health implications, corticosteroids, folic acid, other vitamins and supplements, vaccinations, medications to treat other chronic diseases)

- Infant characteristics:
 - Gestational age at birth
 - Sex
 - Weight
 - Length
 - Head circumference
 - Birth order (for multiple births), and number of fetuses

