 - Laboratory values, if available (e.g., CD19, neutrophil, lymphocyte, white blood cell, immunoglobulin and platelet counts)
 - Apgar scores (1, 5, and 10 minutes)
 - Congenital malformations noted (including description and attribution)
 - Vaccination information
 - Whether infant is breastfed
- SAEs related to pregnancy (as per [Section 11](#))
- All infant SAEs (including serious and severe infections of NCI CTCAE severity Grade 3, and hospitalizations other than for standard post-birth hospital stay)

Pediatric follow-up (approximately at 12, 26, and 52 weeks after birth):

- Reporter of information (patient, obstetrician, infant HCP)
- Infant characteristics:
 - Feeding behavior (including breastfeeding)
 - Weight
 - Length
 - Head circumference
 - Developmental milestones (e.g., social/emotional, language/communication, cognitive, movement/physical development milestones, as defined by the CDC [\[2016\]](#))
 - Laboratory values, if available (e.g., CD19, neutrophil, lymphocyte, white blood cell, immunoglobulin and platelet counts)
 - Evidence of any new congenital malformation since last follow-up
 - Vaccination information
 - All infant SAEs (including serious and severe infections of NCI CTCAE severity Grade 3, and hospitalizations other than for standard post-birth hospital stay)

Early termination of study participation contact, if applicable:

- Reporter of information (patient, obstetrician, infant HCP)
- Assessments appropriate for the time of withdrawal
- Reason for study withdrawal

- Ocrelizumab treatment (including start and stop dates, dose, dosing frequency, reason for discontinuation (if applicable))
- Other medications (including other MS treatments such as glatiramer acetate, teratogenic medications or medication with potential fetal health implications, corticosteroids, folic acid, other vitamins and supplements, vaccinations, medications to treat other chronic diseases)
- Pregnancy status:
 - Gestational age
 - Any prenatal testing performed and results (e.g., rubella titer, toxoplasmosis, venereal disease research laboratory test, hepatitis screen, ultrasounds, amniocentesis, maternal serum alpha-fetoprotein screen, glucose screen)
 - Pregnancy outcome, if applicable (per [Section 9.3.2](#), e.g., elective or therapeutic termination, spontaneous abortion, ectopic pregnancy, molar pregnancy)

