9.4.2 Data Collected during the Observation Period

After a patient provides consent, the CC will obtain demographic and contact information in addition to baseline information at the time of enrollment. All patient and HCP contact information will be confidential and will remain at the CC. The CC will then contact the patient each trimester to update contact information and ascertain the occurrence of pregnancy outcomes or other events (see [Section 9.3](#) for list of variables). Below is a list of the expected contacts with patients and HCPs:

Expected contacts with patient:

- Enrollment
- End of Trimester 1 (approximately 14 gestational weeks)
- Mid-Trimester 2 (approximately 21 gestational weeks)
- Mid-Trimester 3 (approximately 34 gestational weeks)
- EDD plus 4 weeks
- Birth plus 12 weeks, 26 weeks, and 52 weeks (live births only)

Expected contacts with the patient's HCP (neurologist, obstetrician):

- Enrollment
- Mid-Trimester 2 (approximately 21 gestational weeks)
- EDD plus 4 weeks

Expected contacts with the infant's HCP (live births only):

- EDD plus 4 weeks
- Birth plus 12 weeks
- Birth plus 26 weeks
- Birth plus 52 weeks

[figure not shown]
After a patient is enrolled, there will be at least three attempts made to contact the patient and/or the HCP via phone, e-mail, fax, and mail, as appropriate, approximately 10 business days apart. If data is obtained after a follow-up interval is passed, the CC will accept and enter the data and continue follow-up of the patient. If an HCP is not responsive at the time points described above, the patient will be asked to provide the information contained on the HCP worksheets. If the HCP then responds to contact, their information will supersede the patient-reported information. At all time points, the type of reporter (patient, obstetrician, neurologist, or infant HCP) will be recorded.

In the routine care setting, patients are seen regularly by their treating physicians either for treatment or for regular assessment after treatment. Thus, no study-specific visits or evaluations are required by this protocol.

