If the patient experiences an adverse pregnancy outcome or has an elective or therapeutic termination or a termination of unknown cause, the HCP and patient will be encouraged to report the outcome to the CC as soon as possible. In the event of an elective or therapeutic termination, spontaneous abortion, fetal death or stillbirth, communications with the patients will cease after pregnancy outcome information has been obtained.

See [Figure 1](#) for data collection overview.

Figure 1 Data Collection Overview

See [Appendix 2](#) for the data collection overview (as per standard of care) during the treatment period.

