11.1.2.1 Serious Adverse Event Reporting Period

The CC will seek information on pregnancy related SAEs at each patient and HCP contact. All SAEs related to pregnancy, pregnancy outcomes, and infants, whether reported by the patient or by HCPs, will be recorded in the SAE section of the eCRF.

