Appendix 2 Data Collection Overview (as per Standard of Care)

Data Collection ^a	Enrollment	Prenatal Follow-Up			Pregnancy Outcome	Pediatric Follow-Up	Early Termination of Study Participation Contact
		End 1st Trimester (~14 weeks)	Mid 2nd Trimester (~21 weeks)	Mid 3rd Trimester (~34 weeks)	~4 weeks after EDD	Infant Age 12, 26, and 52 Weeks	End of Patient Participation in Study
Informed consent ^b	x						
Inclusion/exclusion criteria	x						
Patient demographics and characteristics	x						
Medical history	x						
MS disease and treatment history	x						
Pregnancy history, and current pregnancy information ^c	x						
Lifestyle factors ^d	x	x	x	x	x		
Prior and concomitant medications ^e	x	x	x	x	x		
Ocrelizumab treatment ^f	x	x	x	x	x		x
Comorbid conditions	x	x	x	x	x		
MS disease status ^g		x	x	x	x		
Current pregnancy status		x	x	x			x ^h
Gestational age (weeks)		x	x	x	x		x ^h
Pregnancy outcome ⁱ					x		x ^h
Infant characteristics					x ^j	x ^k	x ^h
Infant abnormalities ^l					x	x	x ^h
SAEs related to pregnancy,	x	x	x	x	x	x	x ^h

Data Collection ^a	Enrollment	Prenatal Follow-Up			Pregnancy Outcome	Pediatric Follow-Up	Early Termination of Study Participation Contact
		End 1st Trimester (~14 weeks)	Mid 2nd Trimester (~21 weeks)	Mid 3rd Trimester (~34 weeks)	~4 weeks after EDD	Infant Age 12, 26, and 52 Weeks	End of Patient Participation in Study
pregnancy outcome, or infant SAEs and severe infections (NCI CTCAE Grade 3) in infants ^m							
Reason for early termination of study participation							x

EDD = expected date of delivery; EDSS = Expanded Disability Status Scale; LMP = last menstrual period; MS = multiple sclerosis; SAE = serious adverse event; NCI CTCAE = National Cancer Institute Common Terminology Criteria for Adverse Events

- ^a Available data will be collected; no additional diagnostic or monitoring procedures shall be applied to the patients outside of routine clinical practice.
- ^b Written or verbal informed consent must be obtained before any data collection (per local regulations or ethics committee requirements). If the patient is a minor, written consent must be obtained from the parent or legal guardian.
- ^c Including previous pregnancy outcomes, detailed family history including pregnancy complications, adverse pregnancy outcomes and developmental abnormalities, and information about baseline risks.
- ^d Including smoking, use of caffeine, use of alcohol, and use of recreational drugs.

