- ^e Prior and concomitant medications up to 6 months prior to LMP.
- ^f Start and stop dates, dose, dosing frequency, reason for discontinuation (if applicable)
- ^g MS disease status and MS relapses since enrollment including EDSS, if available
- ^h If applicable
- ⁱ Including live births, spontaneous abortions, stillbirths, elective or therapeutic terminations, reason for elective or therapeutic termination (e.g., prenatal testing finding, risk to mother's health, undesired pregnancy), and autopsy results and pathology reports, if available
- ^j Gestational age, sex, weight, length, birth order (for multiple births), Apgar scores, breastfeeding status, and any congenital malformation noted, including description and attribution.
- ^k Including postnatal growth and development: feeding behavior, weight, length, developmental milestones, breastfeeding status, evidence of any abnormality, and outcomes possibly related to immune suppression/immune mediated mechanism (neutropenia, lymphopenia, leukopenia, decreased B-cell counts, hypogammaglobulinemia, inadequate vaccine response [including low vaccine-induced response titers] and thrombocytopenia), if applicable.
- ^l Detailed information on any infant abnormalities identified after infant birth.
- ^m Reported throughout the study or until study discontinuation as applicable

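### Section 11.1.2 stops collecting pregnancy-related SAEs when the outcome is reported, so postpartum maternal capture depends on a reporting date and conflicts with 11.1.2.1 and the 12-week maternal-death window

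*Protocol*

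**What the plan says.** The protocol deals with the period for maternal (pregnancy-related) SAEs in several places.

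- **Section 11.1.2:** "SAEs related to pregnancy will be collected until the end of her observation period, i.e. until a pregnancy outcome is reported", unless the woman withdraws before then. Infant events continue through the first year.
- **Section 11.1.2.1**, the subsection on the SAE reporting period: "The CC will seek information on pregnancy related SAEs at each patient and HCP contact". No end date is given.
- **Section 9.4.2:** for live births the mother's own contacts continue to "Birth plus 12 weeks, 26 weeks, and 52 weeks (live births only").
- **Section 9.3.2.3:** the contact headed "Birth outcome follow-up (approximately 4 weeks after EDD") includes pregnancy-related SAEs and refers to Section 11. The synopsis and Appendix 3 Table 3 do the same. The pediatric contacts in 9.3.2.3 and Appendix 3 Table 4 list infant SAEs only.
- **Section 9.3.2.2.15:** maternal deaths are reported for up to 12 weeks after delivery. Appendix 4.3.5 ties the recording of deaths as SAEs to the period in 11.1.2.1.
- **Appendix 2:** one row combines pregnancy-related SAEs with "pregnancy outcome, or infant SAEs and severe infections (NCI CTCAE Grade 3) in infants". It is marked through the 12, 26 and 52 week contacts, with the footnote "Reported throughout the study or until study discontinuation as applicable".
- **Section 9.4.2, after a loss or termination:** "communications with the patients will cease after pregnancy outcome information has been obtained".

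**The concern.** A collection window that closes on a report has no fixed length. Two women with the same postpartum complication on the same day after delivery can be handled differently because one outcome was reported at delivery and the other at the scheduled contact. Section 11.1.1.1 counts a delivery hospitalization as a pregnancy-related SAE when a complication prolongs it, so the protocol does mean to capture serious complications that can arise after birth. Under 11.1.2 such an event falls outside collection once the outcome has been reported.

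The same stop falls before the end of the period over which the protocol promises to report maternal deaths. Pregnancy-related SAEs are also most of the maternal safety information in the study database, since Section 11 sends other maternal events to spontaneous reporting. An analysis plan can narrow a window afterwards, but it cannot recover events that were never collected.

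**Working it through.** The protocol states no figure to reproduce. The check sets the passages side by side and adds date arithmetic, with the EDD at 40 weeks and the birth contact held on its nominal date, week 40 + 4 = 44.

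**1. Postpartum weeks of maternal SAE collection under 11.1.2, live birth**

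- Outcome reported at delivery: 0 weeks.
- Outcome first reported at EDD + 4: weeks covered = 44 − gestational age at birth.

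| Birth at (weeks) | Reported at delivery | First reported at EDD + 4 |
|---|---|---|
| 42 | 0 | 44 − 42 = 2 |
| 40 | 0 | 44 − 40 = 4 |
| 37 | 0 | 44 − 37 = 7 |
| 34 | 0 | 44 − 34 = 10 |
| 32 | 0 | 44 − 32 = 12 |

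**2. Against the 12-week maternal-death window (9.3.2.2.15)**

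Shortfall = 12 − weeks covered.

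- Reported at delivery: 12 − 0 = 12 weeks.
- Reported at EDD + 4, birth at 40 weeks: 12 − 4 = 8 weeks.
- Reported at EDD + 4, birth at 37 weeks: 12 − 7 = 5 weeks.

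So for a birth at 37 weeks or later the stop falls before the end of the death window even when the outcome is reported on schedule. A fatal obstetric event in postpartum week 8 is within 9.3.2.2.15. It is also within 11.1.2.1 read literally. It is past the stop in 11.1.2.

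**3. Against 11.1.2.1**

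Asking at every patient contact, with the contacts in 9.4.2, would run to 52 weeks after a live birth. Section 11.1.2 ends at the outcome report. The two adjacent paragraphs do not give the same period, and Appendix 4.3.5 relies on the one that has no end.

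**4. The observation period**

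Section 11.1.2 equates its end with the outcome report. Section 9.4.2, whose heading names the observation period, lists patient contacts to 52 weeks after birth. Stated participation is up to 21 months. 40 + 52 = 92 weeks, and 92 ÷ (365.25 / 12 / 7) = 21.2 months; 40 weeks alone is 9.2 months. Participation therefore continues well past the point that 11.1.2 calls the end.

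**5. Against the birth contact**

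If the outcome is first reported at EDD + 4, the birth contact and 11.1.2 agree. If it was reported before then, 11.1.2 has already closed collection while 9.3.2.3 and Appendix 3 Table 3 still ask for events.

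**The case against.** Much can be said for the protocol.

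- **Appendix 2.** A reader might infer a firm rule that maternal SAEs are collected to 52 weeks. The row also covers infant SAEs, its footnote says as applicable, and the detailed lists for the pediatric contacts name infant SAEs only. The row is ambiguous and does not establish such a rule. This stands.
- **Birth contact.** It is the scheduled outcome report and defers to Section 11, so it conflicts with 11.1.2 only when the outcome was reported before it. This stands.
- **Losses.** Contact ends once outcome information is obtained, which agrees with 11.1.2. A reader might infer that a further contact after a loss is needed. That is a design preference, not a correction. This stands.
- **Comparison between groups.** A reader might infer a biased maternal risk ratio. Pregnancy-related SAEs are not among the outcomes listed in 9.3.2.2, and 9.7.2 names malformation, spontaneous abortion and preterm birth rates for comparison. Follow-up procedures are the same in both groups. Objective 3 mentions maternal outcomes in general terms, but nothing shows that reporting speed or loss frequency differs between groups. The bias is not demonstrated.
- **Reading 11.1.2.1 within 11.1.2.** It could describe how events are sought inside the period just defined, with the maternal-death window as a specific addition. This is possible, but 11.1.2.1 is the subsection named for the reporting period, it states no limit, and Appendix 4.3.5 points to it alone. Even on this reading, the stop in 11.1.2 remains a reporting date, and the death window still lies beyond it.

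**Conclusion.** The conflict is real and limited. Section 11.1.2 makes the maternal SAE window depend on when the outcome is reported. For a live birth it is 0 weeks after delivery if reported at once, and about 4 to 7 weeks for births at 40 to 37 weeks if first reported at EDD + 4. This is inconsistent with 11.1.2.1 and with the 12-week maternal-death window, and with the birth contact when the outcome is reported early. The figures assume that the birth contact takes place on its nominal date.

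The documents give no rate or timing for postpartum obstetric events, so the share that would be missed cannot be stated. They do not support a firm 52-week maternal rule, a biased comparison between groups, or a need for further contact after a loss. Major congenital malformations, the sample size and the power are not affected. The point concerns complete and uniform capture of maternal safety events.

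**What to change.** In 11.1.2, replace the stop at the outcome report with one maternal SAE window for live births, defined by the date of the event and counted from the date of the pregnancy outcome. The length is the sponsor's choice, provided that it is consistent with the 12-week maternal-death window. Then:

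- Align 9.3.2.2.15, 9.3.2.3, 11.1.2 and 11.1.2.1 to it, so that the cross-reference in Appendix 4.3.5 leads to a defined period.
- Split the Appendix 2 row into a maternal and an infant SAE row, and adjust Appendix 3 Tables 3 and 4 to match.
- Summarise maternal SAEs only within that window.
- For losses and terminations, state that capture ends with the outcome contact, and report those women separately.

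The cost is protocol wording plus, if the window outlasts the birth contact, one maternal SAE item at an existing postpartum contact, such as the one at birth plus 12 weeks. Scheduled contacts with the mother's own HCPs end at EDD + 4, so later information would come mainly from the patient. Section 11.1.2.1 already accepts patient reports.

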11.1.2.1 Serious Adverse Event Reporting Period

The CC will seek information on pregnancy related SAEs at each patient and HCP contact. All SAEs related to pregnancy, pregnancy outcomes, and infants, whether reported by the patient or by HCPs, will be recorded in the SAE section of the eCRF.

11.1.2.2 Procedures for Recording Serious Adverse Events

HCPs should use correct medical terminology/concepts when reporting SAEs related to pregnancy and pregnancy outcomes to the CC. Colloquialisms and abbreviations should be avoided.

Only one SAE term should be recorded in the event field of the eCRF.

11.1.3 Reporting Requirements from Physician to Marketing Authorization Holder

11.1.3.1 Immediate Reporting Requirements from Physician to Marketing Authorization Holder

SAEs require immediate reporting to allow Roche and the regulatory authorities to take appropriate measures to address potential new risks associated with the use of the

medicine. The physician must report such events to Roche immediately; under no circumstances should reporting take place more than 24 hours after the physician learns of the event.

If an HCP or a patient reports any non-pregnancy-related SAEs, these SAEs must be forwarded to Roche to process as a spontaneous report for ocrelizumab events and the MAH for glatiramer acetate events. (Refer to local product label for relevant contact details).

The CC will consult with Roche for questions regarding whether an SAE falls into the definition of a pregnancy-related SAE as per [Section 11.1.1.1](#) (i.e., any obstetric complication fulfilling one of the criteria for a SAE).

11.1.3.2 Reporting Requirements for Non-Serious Adverse Events

Selected non-serious AEs will be collected as part of the study database (see [Section 11.1.1](#) and [Appendix 4.3.3](#)). If an HCP or a patient reports any non-pregnancy-related AEs, these AEs must be forwarded to Roche to process as a spontaneous report for ocrelizumab events and the MAH for glatiramer acetate events (refer to local product label for relevant contact details).

11.1.3.3 If EDC System is Temporarily Unavailable

In the event that the EDC system is temporarily unavailable, a completed paper reporting form and fax coversheet should be faxed/scanned to Roche Drug Safety or its designee immediately (i.e., no more than 24 hours after learning of the SAE), using the fax number or e-mail address provided.

Once the system is available again, all information should additionally be entered and submitted via the EDC system.

11.1.4 Follow-Up of Patients after Pregnancy Related Adverse Events

11.1.4.1 Physician Follow-Up

The physician should follow each SAE related to pregnancy until the event has resolved to baseline grade or better, the event is assessed as stable by the physician, the patient is lost to follow-up, or the patient withdraws consent. Every effort should be made to follow all SAEs related to pregnancy considered to be related to ocrelizumab for all relevant information and until a final outcome can be reported.

During the study period, resolution of SAEs related to pregnancy (with dates) should be documented in the SAE section of the eCRF.

